**1. Introduction and Purpose:**

Anticoagulation is essential during extracorporeal membrane oxygenation (ECMO) to prevent catastrophic circuit clotting. Use of unfractionated heparin (UFH) as the standard of care during ECMO was adapted from the knowledge gained from cardiopulmonary bypass. Unfortunately, UFH has several limitations during ECMO. Bivalirudin, a direct thrombin inhibitor, is an alternative and potentially superior anticoagulant for patients on ECMO. Previous studies of bivalirudin use during ECMO have shown that compared to UFH, bivalirudin is safe and may decrease bleeding, decrease blood product transfusion, and decrease ECMO cost [1-4]. Improving anticoagulation during ECMO is critically important as the most common complications during ECMO are secondary to bleeding and clotting [5].

We hypothesize that neonatal and pediatric ECMO patients receiving bivalirudin will spend more time at goal anticoagulation and will experience less hemorrhagic and thrombotic complications when compared to patients receiving unfractionated heparin.

Aim 1: Compare the efficacy of bivalirudin versus UFH during neonatal and pediatric ECMO.

Aim 2: Define the incidence of hemorrhagic and thrombotic complications in patients receiving bivalirudin during ECMO.

Aim 3: Determine the optimal dosing for bivalirudin for effective anticoagulation on ECMO.

The primary outcome of the study will be to compare the percentage of time spent at goal anticoagulation for patients receiving UFH versus patients receiving bivalirudin. Secondary outcomes will include incidence of major bleeding events as defined by the International Society of Thrombosis and Hemostasis including fatal bleeding, intracranial hemorrhage, retroperitoneal hemorrhage, extrasurgical or unexpected surgical site bleeding that causes a decrease of hemoglobin of > 2 g/dL or leads to transfusion of two or more red blood cell transfusions within a 24 hour period, and surgical site bleeding that requires surgical intervention [6, 7]. We will compare the need for blood product transfusion of packed red blood cells, platelets, fresh frozen plasma, cryoprecipitate, and antithrombin III (thrombate) between those who received UFH versus those who received bivalirudin. Lastly, we will describe the median dose needed for bivalirudin in all patients and for those with renal insufficiency and renal failure.

**2. Background:**

Extracorporeal membrane oxygenation (ECMO) is a lifesaving therapy for patients with respiratory and/or cardiac failure. Approximately 1500 to 2000 neonatal and pediatric patients are placed onto extracorporeal membrane oxygenation (ECMO) each year for respiratory failure [8]. At Children's Medical Center, we place approximately 40 neonatal and pediatric patients onto ECMO each year. Despite advancements in ECMO circuit technology such as heparin coated tubing, smaller oxygenators, and improved cannula, hemorrhage and thrombosis are the most common complications during ECMO [8, 9]. Approximately 4-11% of neonatal and pediatric ECMO patients suffer an intracranial hemorrhage and 30% have some form of thrombosis [10, 11]. Hemostatic complications during ECMO are associated

with increased morbidity and mortality [5, 11]. In order to prevent catastrophic circuit clotting, anticoagulation is essential.

As mentioned previously, UFH is currently the standard anticoagulant for ECMO but it has several important limitations. UFH requires antithrombin for maximum therapeutic effect but neonates and critically ill patients are known to be deficient in antithrombin. Besides binding to antithrombin, UFH binds to the ECMO circuit and other plasma proteins altering its pharmacokinetics. The tests used to monitor UFH's clinical effectiveness such as aPTT, ACT and anti-factor Xa are all imperfect tests and have been shown to have variable correlation to themselves and to UFH during ECMO [12-16]. There are no randomized studies that have investigated superiority of UFH over other anticoagulants during ECMO. In addition, there is no universally accepted test or combination of tests to monitor the functional effect of UFH during ECMO.

Bivalirudin is a specific and reversible direct thrombin inhibitor. Bivalirudin binds to both bound free and clot-bound thrombin and unlike UFH it does not require antithrombin. In addition, bivalirudin also has a short half-life of 25 minutes and has low to negligible immunogenic potential. Bivalirudin is currently FDA approved for patients with unstable angina undergoing percutaneous transluminal coronary angioplasty (PTCA), percutaneous coronary intervention (PCI) with use of glycoprotein IIb/IIIa inhibitor, and patients with heparin induced thrombocytopenia undergoing PCI [17]. Bivalirudin is currently used off label for pediatrics.

Bivalirudin has been used off label in children for deep venous thrombosis prophylaxis and treatment, cardiopulmonary bypass, cardiac catheterization and ECMO [17]. An open label study conducted by the manufacture of 110 neonatal and pediatric patients identified the dosing regimen, plasma concentration, and safety profile of bivalirudin. Bleeding occurred in 2 of 110 patients (1.8%) and thrombosis occurred in 8 of 110 patients (7.5%) [18]. At our institution, 6 non-ECMO neonatal and pediatric patients have been initiated on bivalirudin for concern of or confirmed heparin induced thrombocytopenia. In the six patients there were no thrombotic or hemorrhagic complications.

Pediatric ECMO studies using bivalirudin have thus far shown benefit and confirmed safety of bivalirudin but are limited to single case reports, one small case series, and one small retrospective study. Nagle et al described 12 neonatal and pediatric ECMO patients on bivalirudin and found no major bleeding events [1]. The study also defined the maintenance dose need to achieve goal aPTT. A combined pediatric and adult retrospective review compared 21 total patients using bivalirudin to UFH and found that patients receiving bivalirudin had decreased bleeding, decreased blood product transfusion, and decreased pediatric ECMO cost compared to patients receiving UFH [2]. An adult case-control study of 10 patients receiving UFH compared to 10 patients receiving bivalirudin, found that patients receiving bivalirudin had less variation of aPTT and a trend towards decreased number of changes of bivalirudin dose compared to patients receiving UFH [3]. No difference was seen in bleeding or thrombotic complications between the two groups [3]. To our knowledge, there is no prospective study comparing bivalirudin to UFH for pediatric or adult ECMO.

### **3. Concise Summary of Project:**

We will prospectively enroll 30 neonatal and pediatric ECMO patients in the Pediatric Intensive Care Unit and Pediatric Cardiovascular Intensive Care Unit at Children's Medical Center, Dallas campus. The patients will be randomized into two arms; one arm will receive unfractionated heparin and the other arm will receive bivalirudin. There will be 15 patients in each arm for a total of 30 patients. We estimate that we will need to consent 50 patients to achieve our goal of 30 enrolled patients. Enrollment and completion of this study will require approximately two years.

After consent is obtained, patients will be randomized into either the unfractionated heparin group or bivalirudin group. The UFH group will be given UFH as is currently standard of care at Children's Medical Center. A bolus of UFH will be given on initiation and the UFH infusion will be titrated throughout the entire ECMO run based on combination testing of anti-factor Xa, aPTT, and thromboelastogram (TEG).

The bivalirudin group will receive an UFH bolus during cannulation and UFH infusion until consent obtained (maximum time of 24 hours) and then transitioned immediately from UFH infusion to bivalirudin infusion. Once initiated, the bivalirudin infusion will be titrated based on aPTT.

Bivalirudin's trade name is ANGIOMAX® and is manufactured by The Medicines Company. Bivalirudin directly inhibits thrombin by binding to the free and clot-bound thrombin. It is stored in a single-dose vial with 250 milligrams of bivalirudin to be reconstituted with sterile water. After reconstitution it may be stored at 2-8°C for up to 24 hours. It is excreted predominantly through proteolysis with 20% cleared renally. Patients with renal insufficiency or failure required a decrease in infusion rate based on creatinine clearance.

ECMO circuit tubing will be collected at time of circuit tubing change or at the end of ECMO. Normally, the used circuit tubing system is discarded in the appropriate biohazard waste container. For this study, will analyze the circuit tubing after it has been removed from the patient. After removal, the circuits will be drained and filled with normal saline (to prevent further clotting) by one of the ECMO team members or one of our study team members. The steps involved are detailed in the paragraphs below and will be covered by study finances and not billed to the patient in any way.

The cannula with the circuit tubing system attached is cut away from the patient per standard of care and the circuit is drained of blood. The A-V loop (arterial venous) is created using a T-connector (1/4 x 3/8 inch size) and connected to the circuit. A 1 liter bag of normal saline is run through the circuit until the fluid looks clear with the exception of clots, or fibrin strands, already adhering to the tubing. The bridge ports are then capped and the circuit is placed in a biohazard bag.

After removal of the circuit from the patient, the blood will be appropriately drained into a biohazard bag. The circuit will be filled with normal saline and stored in a biohazard bag. The circuit and the biohazard bag will be labeled with the patient study ID and date. There will be no patient identifiers on the circuit, biohazard bag, or shipment label. The biohazard bag will then be stored in a dedicated storage area that is locked with badge-access entrance only. The circuits will be shipped in the red biohazard bags, in a standard FedEx cardboard box (flushed circuits are non-infectious), with the appropriate shipping label for shipment to Biotechnology Building (IBB) at the Georgia Institute of Technology. The individual responsible for receiving the study circuits is [name].

For the primary outcome, all aPTT and anti-factor Xa values (for the UFH group only) will be recorded during the ECMO run. Hemorrhagic complications will be defined using the International Society of Thrombosis and Hemostasis major bleeding criteria. Blood product transfusion will be recorded in ml/kilogram/ECMO day. Thrombosis will be defined as need for circuit change and clot burden in the ECMO circuit. A clot burden score will be performed on each patient every 6 hours. ECMO cost will include cost of the circuit, cost of blood products including antithrombin, cost of circuit change, and cost of anticoagulant.

Patients in the UFH arm may cross over into the bivalirudin arm if they develop heparin induced thrombocytopenia or heparin resistance defined as UFH dose of > 70 u/kg/hour with inability to obtain goal Xa or aPTT. Bivalirudin patients may cross over into the UFH arm if they are unable to achieve adequate anticoagulation and have continued development of thrombosis in the circuit or the patient or if the patient develops an intracardiac thrombus. The primary team or parent/guardian can withdraw the patient from the study for any reason at any time.

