Patients in the UFH arm may cross over into the bivalirudin arm if they develop heparin induced thrombocytopenia or heparin resistance defined as UFH dose of > 70 u/kg/hour with inability to obtain goal Xa or aPTT. Bivalirudin patients may cross over into the UFH arm if they are unable to achieve adequate anticoagulation and have continued development of thrombosis in the circuit or the patient or if the patient develops an intracardiac thrombus.

Randomization:

Patients will be randomized 50/50 into the bivalirudin group or the heparin group. Each group will have 15 patients for a total of 30 patients. Randomization will occur via a sealed envelope assignment.

Research related costs:

Version 1.3 13JUN2018

Thrombin generation assay will be performed on day one and on day three for patients in both arms. The patients will not be responsible for the cost of the test. In addition, per current standard of care at Children's echocardiograms will be performed at time of cannulation and as needed to evaluate cardiac function and/or cannula position. If an echocardiogram is performed on patients in the bivalirudin arm to evaluate for intracardiac thrombus, the patient will not be responsible for the charge.

Patients will be responsible for all standard ECMO related costs including blood product transfusion and anticoagulant. The average wholesale price of bivalirudin for a 250mg vial is \$609. On average one vial per day will be used per patient. The average wholesale price of unfractionated heparin for a 250ml bag is \$20. The entire bag or portion of bag will be used per day per each patient. Therefore, the patients in the bivalirudin arm may incur a higher cost.

Data will be collected on the patients from time of ECMO cannulation to time of hospital discharge. Blood draws for the both groups of patients will follow current CMC protocol for ECMO except that bivalirudin patients will not get anti-factor Xa testing. The only additional test will be a thrombin generation assays. Thrombin generation assays will require an extra 5.4 ml total of blood. In addition, blood samples for dilute thrombin time, ecarin chromogenic assay, bivalirudin level and aPTT will be frozen and stored for future analysis after study completion. Samples will be drawn daily, and obtained from leftover SOC coagulation labs drawn per protocol so no additional blood sampling will be required. Patients will not be responsible for the cost of this analysis.

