#### **8. Sources of Research Material:**

The electronic medical records of each enrolled patient will be accessed to obtain demographic data, laboratory values, echocardiogram reports, imaging reports, blood product transfusion requirements, and disposition. All study documents containing patient information will remain password protected. Only study personnel will have access to the study records.

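### Thrombosis is defined only by circuit events, so a thrombus in the patient without a circuit event is not classified as thrombosis under the written definition

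*Combined protocol and SAP*

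**What the plan says.** Section 3 (Concise Summary of Project) holds the only definition of thrombosis in the supplied documents: "Thrombosis will be defined as need for circuit change and clot burden in the ECMO circuit". The next sentence sets the measurement schedule: "A clot burden score will be performed on each patient every 6 hours". No scale or event threshold is given for the score.

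The outcome serves two statements in section 1. The hypothesis is that bivalirudin patients "will experience less hemorrhagic and thrombotic complications when compared to patients receiving unfractionated heparin". Aim 2 is to "Define the incidence of hemorrhagic and thrombotic complications in patients receiving bivalirudin during ECMO". The secondary outcomes listed in section 1 define major bleeding in detail but do not define thrombosis. Section 14 lists the incidence of clotting events among the outcomes to be analysed, without defining them.

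Thrombosis in the patient does appear elsewhere. The cross-over rule, given in section 3 and again in section 4, includes "continued development of thrombosis in the circuit or the patient or if the patient develops an intracardiac thrombus" among the grounds for moving a bivalirudin patient to heparin. Section 10 describes a theoretical increase in the risk of intracardiac thrombus when flow is stagnant, provides for echocardiograms when there is clinical concern, and says that such a patient is switched to heparin. Section 8 lists "echocardiogram reports, imaging reports" among the source material.

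**The concern.** The authors distinguish circuit thrombosis from patient thrombosis when they write the cross-over rule, but they do not carry the distinction into the outcome definition. A bivalirudin patient could develop the complication named in section 10, cross over because of it, and appear in the results as a crossover with no thrombotic event.

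Two results are exposed. The Aim 2 incidence in bivalirudin patients could be too low. The hypothesised comparison of thrombotic complications could leave out a thrombotic harm that the protocol itself anticipates. The bleeding outcome, by contrast, counts harm in the patient, including fatal and intracranial bleeding. Setting bleeding against thrombosis would then weigh patient events against equipment events. Section 13 says that a multicenter trial is to follow, depending on the pilot's results, so an understated incidence could carry forward.

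**Working it through.** The plan gives no figure for this point, so there is nothing to reproduce. The check is a comparison of the text, followed by a small calculation of scale.

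**1. Is patient thrombosis counted anywhere?**

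| Place | What it covers | Does it count patient thrombosis as an outcome? |
|---|---|---|
| Section 1, hypothesis and Aim 2 | Thrombotic complications, no location given | Implied, not defined |
| Section 3, definition | Circuit change; clot burden in the circuit | No |
| Section 3, score every 6 hours | Clot burden, which the sentence before ties to the circuit | No |
| Sections 3 and 4, cross-over | Circuit, patient and intracardiac thrombus | No; a ground for cross-over |
| Section 10 | Intracardiac thrombus | No; a risk and a reason to change treatment |
| Section 14 | Clotting events | Undefined |
| Section 11 | Refers to the DSMP | Not supplied, cannot be judged |

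**2. Apply the definition to the possible patients.**

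- Circuit event, with or without patient thrombus: classified as thrombosis through the circuit.
- Patient thrombus, no circuit event: not classified.
- Neither: not classified.

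Only the second row is the gap. Its size depends on what counts as a circuit event, and section 3 leaves that open in two ways. It does not say whether circuit change and clot burden are each sufficient or are required together, and it does not say what score is an event. If any visible clot qualifies, some patients with a thrombus are already counted through the circuit. If both components are required, fewer are.

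**3. Weight of one patient.** Section 3 gives 15 patients per arm.

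- 1/15 = 0.0667, or 6.7 percentage points.
- Exact (Clopper-Pearson) 95% interval for 0/15: 0 to 1 − 0.025^(1/15) = 0.218, or 0 to 21.8%.
- Exact 95% interval for 1/15: 0.0017 to 0.3195, or 0.2% to 31.9%.

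These figures hold for any yes/no event in an arm of 15. They show how much one reclassified patient moves the result, not how many patients would be reclassified.

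**4. Can the number affected be estimated?** Section 2 says that "30% have some form of thrombosis". If that rate is assumed to apply to each arm, 15 × 0.30 = 4.5 patients would have some form of thrombosis. Let s be the share with thrombosis in the patient only. The number left out is then 4.5 × s, which runs from 0 (s = 0) to 4.5 (s = 1). The documents do not split the 30% and give no value for s, so this is not an estimate. The 8 of 110 in section 2 is not usable either: the cited study's title places it in children with deep vein thrombosis, and nothing ties the figure to ECMO.

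**5. A side observation.** Sections 3 and 4 say that a patient with an intracardiac thrombus may cross over, while section 10 states the change as definite. These passages must be reconciled, but the classification gap exists on either wording.

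**The case against.** The strongest reply is that this is a gap in labelling and not in data. Echocardiogram and imaging reports are collected, data run to hospital discharge (section 4), intracardiac thrombus is a named ground for cross-over, and the DSMP may cover these events. This stands against one reading that a reader might infer: that patient thrombi would go unrecorded. The documents do not support that. What they lack is a rule that classes such events as thrombosis. Neither an undefined term in section 14 nor a separate safety plan supplies that rule. Leaving the choice to the analyst is what a definition is meant to prevent.

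A second reply is that a circuit outcome is a reasonable choice, because it is scored on one schedule in every patient, whereas patient thrombosis is looked for on clinical concern. That is a good reason to keep a circuit component and to report the two separately. It does not explain why the hypothesis and Aim 2 are worded more broadly. Nor does it make the circuit component complete, since a scoring schedule does not define an event.

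A third reply is that the consequence is limited: thrombosis is not in the section 1 list of secondary outcomes, and this is a pilot of 30 patients. That bears on weight. Thrombotic complications are still part of the hypothesis and of Aim 2.

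**Conclusion.** The point holds. Under the only written definition, a thrombus in the patient without a circuit event is not thrombosis, and no other supplied text says that it is counted. Aim 2 incidence can be understated, and the comparison of thrombotic complications can omit a harm named in section 10. It should be fixed, but it does not touch the primary outcome, time at goal anticoagulation.

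Two stronger conclusions should not be drawn. One is that the definition favours bivalirudin. Patient thrombosis is left out in both arms, and no rate is given for either, so the net direction is unknown. The other is that 6.7 points is the size of the bias. It is the weight of one patient in an arm of 15, and the number of such patients cannot be estimated.

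The conclusion assumes that section 3 is applied as written and that no unsupplied document redefines the outcome.

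**What to change.** In section 3:

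- Add a second, separately reported component: imaging-confirmed thrombosis in the patient (intracardiac, arterial or venous), taken from the echocardiogram and imaging reports already collected.
- Report it descriptively by randomised arm, including events that lead to cross-over.
- Keep the circuit component, but state whether circuit change and clot burden are each an event or are required together, and what clot burden score counts as an event.

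In section 14, define clotting events as these two components, each reported on its own.

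The cost is one added definition, two clarifications and a few case-report fields. No extra test is needed, and treatment does not change.

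The downside is uneven ascertainment. Echocardiograms for thrombus depend on clinical concern (section 10). The charge waiver is stated for one arm only: "If an echocardiogram is performed on patients in the bivalirudin arm to evaluate for intracardiac thrombus" (section 4), the patient is not charged. MRI comes only after decannulation (section 11). Detection may therefore differ by arm. For that reason patient thrombosis should not be merged with the circuit outcome into one comparison, and the limitation should be stated in the plan and in the report.

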#### **4. Study Procedures:**

##### Unfractionated heparin group:

Patients in this group will receive UFH anticoagulation as is current standard of care at Children's. During cannulation a bolus dose of 50-100 units/kg of intravenous UFH will be given. A continuous UFH infusion based on age will be initiated once ACT is < 300 seconds. Infants less than one year will receive a starting dose of 28 units/kg/hour and children > 1 year will receive a starting dose of 20 units/kg/hour per current Children's protocol.

The UFH infusion will be titrated based on targeted anti-factor Xa, aPTT, and thromboelastogram. Labs will be drawn per current standard of care as noted below.

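### Clot burden is scored on the running circuit with no masking described, while de-identified removed circuits already go to an outside laboratory that could supply a masked reading

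*Combined protocol and SAP*

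**What the plan says.** Section 3 (Concise Summary of Project) defines the outcome: "Thrombosis will be defined as need for circuit change and clot burden in the ECMO circuit". The next sentence gives the schedule: "A clot burden score will be performed on each patient every 6 hours". It does not say who scores, on what scale, or whether the scorer is masked.

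No blinding is described anywhere in the document. Section 4, under Randomization, says "Randomization will occur via a sealed envelope assignment". The arms are then managed differently:

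- Bivalirudin (Section 3): "Once initiated, the bivalirudin infusion will be titrated based on aPTT".
- Heparin (Section 4): "The UFH infusion will be titrated based on targeted anti-factor Xa, aPTT, and thromboelastogram".
- Testing (Section 4, Research related costs): "bivalirudin patients will not get anti-factor Xa testing".

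Section 3 also describes what happens to used circuits. They are collected when the tubing is changed or when ECMO ends, and "For this study, will analyze the circuit tubing after it has been removed from the patient". They are flushed with saline in a way meant to leave adherent clot and fibrin in place, labelled with study ID and date, and shipped to an outside university. On identification: "There will be no patient identifiers on the circuit, biohazard bag, or shipment label". Section 14 (Biostatistics) names clotting events among the outcomes but does not mention the circuit analysis.

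**The concern.** A clot score read by someone who knows the treatment can move with expectation. The protocol supplies expectations in both directions: Section 1 hypothesises fewer thrombotic complications on bivalirudin, and Section 10 warns of a theoretical risk of intracardiac thrombus on bivalirudin when blood flow is stagnant. Scoring four times a day does not average such a shift away, because the same tendency enters each score. A difference in clot burden between the arms could then be a drug effect, an assessor effect or both, and the planned data would not separate them.

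Thrombosis is part of the hypothesis and of Aim 2, and Section 13 says the results are to lead to a multicentre trial. The means of a masked second look are largely in place already, since circuits leave the hospital without patient identifiers. The plan does not say that they are used in that way.

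**Working it through.** The plan gives no figure for this outcome, so there is nothing to reproduce. The sample-size statement in Section 14 (about 10 per arm) concerns the primary outcome and does not bear on the point. The check is a comparison of the text, followed by an illustration of scale.

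**1. Can the scorer know the arm?** A score made on each patient every 6 hours must be made on the circuit in use. The infusions have different names, different titration tests and different sampling intervals, and one arm has no anti-factor Xa results. Assignment is by envelope, and no masking step follows. That the trial is open-label and that the score is made at the bedside are inferences, but no other reading fits these procedures. (Section 2 uses the term open label only for the manufacturer's earlier study.)

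**2. Could the laboratory be masked?**

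| Needed for a masked reading | What Section 3 provides |
|---|---|
| Specimen from each circuit | Tubing collected at change or end of ECMO |
| Clot preserved | Adherent clot and fibrin left after the flush |
| No identity on the specimen | Study ID and date only |
| Reader away from the bedside | Outside university laboratory |
| Reader not told the arm | Not stated |
| ID does not encode the arm | Not stated |
| Defined clot measurement | Not stated |
| Link to the thrombosis outcome | Not stated |

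The first four are planned. The last four are missing, and all four are matters of specification.

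**3. How much could a scoring shift matter?** Inputs: n = 15 per arm (Section 3). The two-sided 5% level, the t-test on one summary score per patient, and the shift b in SD units are assumptions. With no true difference, the test statistic follows a noncentral t distribution with 15 + 15 − 2 = 28 degrees of freedom and noncentrality δ = b / √(2/15). The rejection rate is P(|T| > 2.048).

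| Assumed shift b (SD) | δ | Rejection rate |
|---|---|---|
| 0 | 0 | 5.0% |
| 0.2 | 0.548 | 8.3% |
| 0.3 | 0.822 | 12.5% (12.47%) |
| 0.5 | 1.369 | 26.2% |

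Rounded to whole percentages, these are 8%, 12% and 26%, against the nominal 5%.

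**The case against.** The strongest reply is that the laboratory reading is no clean substitute for the score. Most of that reply stands.

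- **The analysis is undefined.** The documents do not say that the laboratory measures clot, and they speak of tubing without saying whether the oxygenator is included. A reading rule would have to be written, so the change is slightly more than a sentence about masking.
- **Timing stays unmasked.** When a circuit is removed, and so how many circuits a patient contributes, depends partly on the unmasked decision to change it. The flush is also judged by eye, by ECMO or study staff with no stated masking.
- **Information is lost.** One reading per flushed circuit misses loose clot and the time course.
- **Exposure is mixed.** A circuit in the bivalirudin arm may have carried heparin for up to 24 hours first, and crossover is allowed both ways.

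For these reasons a reader might infer that the laboratory reading, adjusted for circuit hours, should replace the 6-hourly score. The documents do not support that. Replacement would discard the time course, and circuit hours are a post-randomisation quantity that both treatment and unmasked change decisions can affect. Conditioning on them in the main comparison could introduce bias of its own.

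A reader might also infer that the laboratory result is excluded from the thrombosis outcome, or that the score is shown to be subjective. The text is silent on both. The gap is one of specification.

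It is also fair to say that Section 1 does not list thrombosis among the secondary outcomes, that Aim 2 is worded as a description of incidence, and that no t-test on a clot score is planned. These points lower the priority. They do not remove the gap, because the hypothesis in Section 1 compares thrombotic complications between the arms.

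**Conclusion.** The concern holds in a limited form. One part of the thrombosis outcome is scored on the running circuit with no masking described, in a trial where staff can be expected to know the arm. A route to a masked reading exists but is not specified as one.

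The documents give no basis for sizing the bias. The range of 8% to 26% rests wholly on assumed shifts of 0.2 to 0.5 SD and on a simple t-test at 15 per arm. The gap in the plan does not depend on those figures.

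It would be wrong to read this as a threat to the main result, since the primary outcome is built from laboratory values. The other part of the thrombosis outcome, need for circuit change, has no stated criteria and would stay unmasked whatever the laboratory does. Section 11 refers to a separate data safety and monitoring plan that was not available; masking might be described there. This is an optional, cheap improvement.

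**What to change.** In Section 3, state that the receiving laboratory is not told the allocation and that study IDs do not encode it. Prespecify the laboratory's reading of adherent clot on each removed circuit as a masked clot-burden measure, with a short written reading rule that covers which components are read, patients with several circuits, and circuits that are lost.

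In Section 14, state that this reading is compared by randomised arm, whatever drugs the circuit was exposed to, and is reported beside the 6-hourly score. Keep the 6-hourly score as planned, and state who makes it and on what scale. Report circuit hours by arm descriptively, or adjust for them only in a sensitivity analysis.

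**Cost:** a few sentences and a short reading rule. If the laboratory's planned analysis is not a clot measurement, some reading effort is added. Collection, flushing, labelling and shipping are already planned and, by Section 3, paid from study funds. No patient's care changes.

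**What it does not cure:** loose clot and time course are absent from the masked reading, circuits may have seen both drugs, and the decision to change a circuit remains unmasked.
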